Randomly eligible participants who have provided informed written consent will be recruited. Participants will then be allocated to one of the study regimens in a ratio of 1:1.

1. **Intervention:** BCG vaccine, single dose
2. **Control regimen:** placebo, single dose.

In the BCG clinical trial, participation in the study will last 6 months: during the first 4 months, or for the duration of the recruitment period, participants will receive the randomly designated BCG regimen or only control group. After the recruitment period, all study participants should have received BCG or placebo, and both groups will be monitored through clinical and laboratory examination for 6 months of follow-up. Biosafety care to combat COVID-19 adopted in the participating Health Units will also be monitored during the study period.

Comparator:

The natural evolution of SARS-CoV-2 infection in health professionals will be used to evaluate the efficacy of bcg use as preventive therapy, considering the use of specific vaccines against COVID-19, the time of positivity of COVID-19 tests and the evolution to severe forms of COVID-19.

Specific vaccines against SARS-CoV-2:

- Coronavac® (Sinovac® / Butantan Institute):

The vaccine developed by the Sinovac laboratory® in partnership with the Butantan Institute is a vaccine containing the inactivated SARS-CoV-2 virus. Seroconversion studies of the Sinovac/Butantan vaccine showed results of >92% in participants who took both doses of the vaccine within 14 days and > 97% in participants who took both doses of the vaccine within 28 days.

The efficacy of this vaccine was demonstrated in a regimen containing 2 doses with an interval of 2 weeks. For the prevention of symptomatic cases of COVID-19 that required outpatient or hospital care, efficacy was 77.96%. There were no serious cases in vaccinated subjects, compared to 7 severe cases in the placebo group.

Considering the absence of co-administration studies, covid-19 vaccines are currently not recommended simultaneously with other vaccines. Thus, a minimum interval of 14

days is recommended between COVID-19 vaccines and the different vaccines of the National Vaccination Calendar.

- Covishield® (AstraZeneca® / Fiocruz):

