The vaccine developed by the AstraZeneca/University of Oxford laboratory and produced in partnership with Fiocruz is a vaccine containing 5×10^{10} viral particles (pv) of the replication-deficient chimpanzee recombinant adenovirus vector (ChAdOx1), which expresses the Glycoprotein SARS-CoV-2 Spike (S). Produced in human embryonic brain cells (HEK) 293 genetically modified. After vaccination, in participants who were seronegative at the beginning of the study, seroconversion was demonstrated in $\geq 98\%$ of participants at 28 days after the first dose and $> 99\%$ at 28 days after the second. For prevention of illness by COVID-19 the vaccine demonstrated efficacy of 73% 22 days after the first dose (in a period of at least 3 months) and with strong indication of increased immune response when the second dose is provided within 3 months, which provides an increase of about 7.5 times in levels of humoral response (antibody production). Exploratory analyses showed that increased immunogenicity was associated with a longer dose interval and efficacy is currently more certainly demonstrated for intervals of 8 to 12 weeks. It is notepoint that there were no severe cases or deaths 21 days or more after vaccination, and 10 hospitalizations for severe COVID-19 were observed in the placebo group, including 1 death.

Allocation and randomization:

The randomization process will be carried out centrally and managed by the team of the Ribeirão Preto School of Medicine of USP (FMRP-USP), under the coordination of [name]. The process will be performed using the Microsoft Excel random number generation function®. The result will be composed of a randomization table with size appropriate to the N expected for the study (752 participants) and with a ratio of 1:1, which will be integrated to REDCap prior to the beginning of electronic data collection. The creation and validation of the table will be the responsibility of the data manager/project coordinator.

By including a participant in the study, REDCap will consult the existing randomization table and excel® sequentially to allocated it to one of the groups defined in the study. It is noteworthy that REDCap does not, on its own, perform any form of randomization, which will be based exclusively on the said table in Excel®.

Study visits:

Social networks and electronic media will be used to disseminate the study through folders and calls about the research.

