Adverse reactions were generally lighter and less frequently reported in the elderly (\geq 65 years of age). Analgesic and/or antipyretic medications (e.g., paracetamol-containing products) may be used to provide relief from adverse reactions after vaccination. Adverse drug reactions (ADRs) are organized by MedDRA Organ System Class (SOC). Within each SOC, the preferred terms are organized by decreasing frequency and then by decreasing severity. The frequencies of occurrence of adverse reactions are defined as: very common (\geq 1/10); (\geq 1/100 to < 1/10); unusual (\geq 1/1,000 to < 1/100); rare (\geq 1/10,000 to < 1/1,000); (1< 10,000) and unknown (cannot be estimated with available data).

Risks:

The safety of BCG revaccination among health professionals will be evaluated in order to describe possible injection site reactions and other adverse events.

In addition, we will minimize the occurrence of AS, excluding immunosuppressed individuals or using concomitant medications that impact immune responses.

Local and systemic AEs will be evaluated at relevant times through medical visits, for example in the first 20 minutes after BCG injections and in later visits, either in person or by telephone contact. The EAs will be noted and graduated according to the ANVISA Manual.

Adverse events to the BCG vaccine, more frequent have been abscess and lymphadenopathy, with higher reports for men than for women. The rates of As per 10,000 distributed doses were from 11.6 to 15.4, respectively. Unsupurated regional lymphadenopathy greater than 3 cm, supurated regional lymphadenopathy, cheloid scar, or lupoid reaction may occur. The EAs will be monitored and handled throughout the follow-up visits.

The research centers will also be open and available for extra views in case of adverse events. The manifestations will be recorded in the data collection instruments and will be treated and monitored in hospitals linked to the research centers. Similarly, the events will be notified to the National Immunization Program of the Ministry of Health, informing the batch of the vaccine applied as well as the event that occurred. Participants will receive all care and will be guaranteed assistance.

Benefits:

The results of this study may help define a form of prevention of COVID-19 for health professionals and in the future in the population as a whole.

LABORATORY PROCEDURES:

Blood collection:

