Regarding the effect of BCG vaccine administration on the cumulative incidence of SARS-CoV-2 infection or on severe forms of COVID-19, a single intermediate analysis will be performed when the number of volunteers included has reached half of the total sample scheduled to verify whether the evidence would already be conclusive and would allow the study to be interrupted. For type I error protection, intermediate analysis will use a Z value of 2.78 (Chow & Liu, 2004).

The analyses that will be performed in the intermediate analysis will be restricted to the following outcomes: accumulated incidence of SARS-CoV-2 infection, cumulative incidence of severe forms of COVID-19 and proportion of serious adverse events.

The following rules will be used to indicate early completion of the study after intermediate analysis:

- Significant difference in the effect of BCG judged by comparing the proportions of patients who develop SARS-CoV-2 infection or severe forms of COVID-19 in each arm of the study;

- If the effect of BCG is similar between groups and there is a significant difference in the cumulative proportion of serious adverse events;

The results will be evaluated by the Data and Safety Monitoring Committee, which will express the need to continue the study, based on the vaccine's performance in terms of the incidences of SARS-CoV-2 infection or severe forms of COVID-19 and adverse events.

Independent Data Monitoring and Security Committee:

The Data and Safety Monitoring Committee (CMDS) will be composed of three members not linked to participating institutions, in accordance with the Operational Guidelines for the Establishment and Functioning of Data Monitoring and Safety Committees of the Ministry of Health (2008).

This committee will be responsible for reviewing the protocol and progress of the study in all centers, with real-time meetings by videoconference, as detailed below, and will consist of:

[name] - Physician - Professor, Faculty of Medicine, Federal University of Rio Grande do Sul

[name] - Statistician - Institute of Collective Health Studies of the Federal University of Rio de Janeiro

[name] - Physician - Professor, Faculty of Medicine, Federal University of Minas Gerais

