All EAs will be notified to the local EC by the study coordinator at each centre using their own form. EAs shall also be reported to the coordination of the proposing institution no later than 7 days after notification of the EA.

In the case of adverse events related to bcg vaccine (ulcer with diameter greater than 1 cm, cold subcutaneous abscess, hot subcutaneous abscess, granuloma, regional lymphadenopathy not suppurated greater than 3 cm, suppurated regional lymphadenopathy, cheloid scar or lupoid reaction), the coordination of the proposing institution should be notified to the National Immunization Program of the Ministry of Health.

Serious adverse events (EAG) should be reported immediately to the coordination of the Proposing Institution through telephone contact. From this notification, the EAG must be reported to ANVISA within a maximum of 24 hours by the coordinator of the proposing institution through the agency's electronic portal (Notification Form of Serious Adverse Events in Clinical Trials available on the Electronic Portal of Anvisa > Medicamentos > Clinical Research > Adverse Events > Form for Notification of Serious Adverse Events in Clinical Trials - Notification EC).

All serious adverse events suspected to have been caused by the proposed experimental treatment, including deaths will be reported to CONEP, through notification and within 24 hours.

There will be a review of The EA data every 2 weeks. If adverse events are unexpected or not previously described, case review will be requested through a meeting of the data monitoring and security committee, which should take place in real time by videoconference. Serious adverse events will be immediately flagged to the CMDS for extraordinary analysis also by real-time videoconferencing.

Criteria for discontinuation of the study for safety reasons:

No formal rule will be adopted to interrupt the study for safety reasons. The CMDS may recommend stopping the study, based on the review of interval safety results. The study can only be canceled or discontinued after analysis of the reasons for discontinuity by the institution's ZIP Code or CONEP.

Criteria for discontinuation of experimental treatment in the participants:

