No formal rule will be adopted to discontinuation of experimental treatment in the study participants. The CMDS may recommend this study interruption, based on the review of interval results as described above. Nevertheless, this decision can only be effected after evaluation and approval by the institution's ZIP Code or CONEP.

QUALITY MANAGEMENT:

All studies will be conducted in accordance with the ICH-GCP Guidelines (ICH-GCP E6 R2), as far as possible in the research environment, as well as all national legal and regulatory requirements (as applicable).

BUDGET:

Cost	Value
Legal entity	R\$84,000.00
Bags	R\$160,800.00
Inputs	R\$297,188.57
Other	R\$43,571.43
Capital	R\$14.440,00
Total	R\$600,000.00

SCHEDULE:

The schedule presented below is a schedule, and the study should be started only after approval of the CEP.

Phase	Beginning	End
Submission of amendment to CEP/CONEP	01/08/2021	31/08/2021
Recruitment/Inclusion/Intervention	30/10/2020	31/12/2021
Follow-up of patients	30/10/2020	31/06/2022
Data analysis	31/06/2022	31/09/2022
Reporting/Results	31/09/2022	31/12/2022

REFERENCES:

- Brazil, Ministry of Health 2020. Available in: <https://coronavirus.saude.gov.br/definicao-de-caso-e-notificacao>. Access on 05 February 2021
- Brazil, Ministry of Health 2021. Technical Report - National Vaccination Campaign against Covid-19
- Butantan, 2021. BULLText SAYINGS - HEALTH PROFESSIONAL - Covid-19 adsorbed vaccine (inactivated)
- ANVISA, 2021. VACCINE COVID-19 (RECOMBINANT) INSTITUTE OF TECHNOLOGY IN IMMUNOBIOLOGICALBIO-MANGUINHOS / FIOCRUZ. Available in: https://www.gov.br/anvisa/pt-br/assuntos/noticias-anvisa/2021/bulas-saiba-mais-sobre-as-vacinas-autorizadas-para-uso-emergencial/bula-vacina-covid-19-recombinante_vps_001_21-01-2021.pdf. Access on 12 D February 2021
- Kritski, A; Alves D; G Werneck; Zimmermann, I; M Sanchez; Galliez R; Medronho R. Technical Note from researchers from the Federal University of Rio de Janeiro

(UFRJ), University of São Paulo (USP) and University of Brasília (UnB) March 25, 2020 PANORAMA OF COVID-19. Available in <https://ufrj.br/sites/default/files/img-noticia/2020/03otatecnica25032020.pdf> Last access on April 23, 2020

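### A committee-recommended interruption takes effect only after CEP or CONEP approval, and no temporary safety hold on dosing is written for the wait (cheap improvement, low probability of use)

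*Combined protocol and SAP*

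**What the plan says.** Two neighbouring sections of the combined protocol and SAP govern stopping, and their conditions differ.

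- **Criteria for discontinuation of experimental treatment in the participants.** No formal rule is adopted. The CMDS may recommend an interruption, but "this decision can only be effected after evaluation and approval by the" CEP or CONEP. The CEP is printed as ZIP Code, a translation artefact; the sample storage plan names the CEP/CONEP system correctly.
- **Criteria for discontinuation of the study for safety reasons.** Again there is no formal rule, and the CMDS may recommend stopping. "The study can only be canceled or discontinued after analysis of the reasons for discontinuity by the" CEP or CONEP. The word approval does not appear here.

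The intervention is "BCG vaccine, single dose" (Intervention Plan).

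Other safety provisions are written. "Serious adverse events will be immediately flagged to the CMDS for extraordinary analysis" (Plan for monitoring and analysis of adverse events). The same section sends serious events to ANVISA within 24 hours and suspected related ones to CONEP within 24 hours, and has adverse event data reviewed every 2 weeks. At the single interim analysis, early completion is indicated if efficacy is similar and "there is a significant difference in the cumulative proportion of serious adverse events". Quality Management commits the trial to ICH-GCP "as far as possible in the research environment, as well as all national legal and regulatory requirements".

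**The concern.** With one dose per person, there is nothing left to discontinue in someone already dosed. An interruption can therefore protect only people not yet dosed, and it is useful only if it is prompt. The treatment-discontinuation section makes it wait for an outside decision. The supplied text does not say what happens to the next eligible person in the meantime.

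Because no formal safety rule is adopted, the CMDS recommendation is the main safety brake, and it is the step that waits. At stake is exposure of new participants after an independent committee has advised against it. No estimate, error rate or sample size is affected.

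**Working it through.** The plan gives no figure for this point, so there is none to reproduce. The check has two parts.

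**1. Does any supplied provision act on dosing between recommendation and decision?**

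- Immediate flagging to the CMDS, the 24-hour reports, the 2-weekly review and the CMDS review after every 100 participants carry information up to a recommendation. None governs dosing after it.
- The early-completion rules belong to one interim analysis and contain no hold.
- The ICH-GCP commitment is general and qualified, names no hold, and is not cited in either discontinuation section.
- The MOP is cited for operational detail elsewhere but was not supplied, and neither discontinuation section refers to it.

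So no hold is written in the supplied text.

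**2. How many people might be enrolled in the interval?**

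Inputs from the documents:
- 752 participants, allocated 1:1 (Allocation and randomization).
- Recruitment from 30/10/2020 to 31/12/2021, which is 427 days (Schedule).
- An alternative recruitment period of 4 months, about 122 days (Intervention Plan).
- Up to 10 calendar days between screening tests and inclusion (Study visits).
- BCG adverse events "per 10,000 distributed doses were from 11.6 to 15.4" (Risks).

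Assumptions: uniform accrual, no pause, and review times of 7, 14 or 30 days, because the documents give none.

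Rate = participants / days: 752/427 = 1.76 per day; 752/122 = 6.16 per day. People enrolled = rate × review days, with half allocated to BCG.

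| Assumed review | At 1.76 per day (BCG) | At 6.16 per day (BCG) |
|---|---|---|
| 7 days | 12 (6) | 43 (22) |
| 14 days | 25 (12) | 86 (43) |
| 30 days | 53 (26) | 185 (92) |

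Background events in a 14-day review: the low end is 12.3 × 11.6/10,000 = 0.014, and the high end is 43.1 × 15.4/10,000 = 0.066. These rates concern mainly abscess and lymphadenopathy. A signal strong enough to prompt a stop recommendation could exceed them, so the figures show low prior risk and do not estimate harm.

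People whose screening tests could lapse during a pause: 1.76 × 10 = 18; 6.16 × 10 = 62. Neither is a maximum, because accrual need not be uniform.

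**The case against.** The strongest reply is that this reads a great deal into a poor translation. The approval clause sits under a participant-level heading and refers to interval results in general. Applying it to new entrants is an inference. The section headed for safety asks only for prior analysis and concerns cancelling or discontinuing the study, not pausing it. The MOP may already contain a hold, and the CMDS reviews the MOP before the study starts. People not yet dosed also have other protections: the exclusion criteria, confirmation of eligibility at inclusion, and the option to withdraw before dosing. Finally, an automatic hold gives an advisory committee more weight than the plan does.

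Much of this stands. The two clauses must be kept apart, the other protections are real, and the hold is a governance choice. But the approval clause is an explicit rule, not just silence, and in a single-dose trial it can have practical effect only on people not yet dosed. An unseen manual and a qualified general commitment do not displace it. The hold is temporary and leaves the final decision where the plan puts it.

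A reader might infer that the plan has dosing continue against CMDS advice, or that it forbids the team to pause voluntarily. The documents say neither. Nor do they support the claim that every safety stop needs approval, since the safety section requires only analysis.

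**Conclusion.** The point holds as a cheap improvement with a low probability of use. On its literal wording, a CMDS-recommended interruption waits for CEP or CONEP approval, and the supplied text has no temporary hold for the wait.

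It would matter only if the CMDS made such a recommendation and the team went on dosing. Approval by either body suffices and reporting is fast, so the interval may be short. For scale, an assumed 14-day review would cover roughly 25 to 86 people, about 12 to 43 of them allocated to BCG. That range rests on uniform accrual, two recruitment periods taken from the documents and an assumed review time.

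A reader might infer a material expected harm or an absence of safety oversight. Neither is supported: expected background events in the interval are well below one, and the reporting and review provisions are extensive. The case rests on irreversibility and low cost. Whether a hold is truly missing depends on the MOP.

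**What to change.** Add to the section on discontinuing experimental treatment, with a cross-reference in the section on discontinuing the study for safety reasons:

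> When the CMDS recommends stopping or interrupting for safety, new randomisations and any dosing not yet given are suspended temporarily at all centres, by blocking allocation in REDCap and by direct instruction to the centres, and the CEP/CONEP are notified within 24 hours; permanent discontinuation or resumption follows their review.

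"The randomization process will be carried out centrally" through a table read by REDCap, so one action can stop new allocations at all three centres. It cannot stop a dose for someone already allocated, which is why the direct instruction is needed. If the MOP already has such a hold, citing it in both sections is enough.

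The cost is one sentence, one cross-reference and matching MOP text. If the trial then continues, there is a short recruitment pause and repeat screening for people who pass the 10-day window, roughly 18 to 62 depending on accrual. Sample size, error rates and analyses do not change.
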